1. PROTOCOL SUMMARY

Title	Implementation Strategies for Monitoring Adherence in Real Time (iSMART)
Short Title	iSMART Trial
Co-Principal Investigators	[name], MSW, MPH [name], MSHP
Co-Investigators	[name] [name] E. [name] [name], MSCE
Design	Prospective, randomized controlled trial
Objectives	
 • Aim 1: To test the effects of a mobile phone-based chatbot (“Penny”) to improve adherence to oral targeted therapies in approximately 170 patients with non-small cell lung cancer. • Aim 2: To use mixed methods approaches with 30 clinicians and 30 patients to explore factors shaping the acceptability, effectiveness, and future implementation of Penny into routine cancer care.
Trial Duration	Estimated 12 months (December 2020-November 2021)
Study Sites	The University of Pennsylvania Health System
Sample Size	Estimated 170 patients and 30 clinicians
Patient Trial Eligibility	
 • Adult patient (age > 18 years) with advanced NSCLC at recruiting site at UPHS who is receiving one of the following oral therapies: afatinib, erlotinib, dacomitinib, gefitinib, osimertinib, alectinib, brigatinib, crizotinib, or lorlatinib • Patient possession of a mobile device that can send/receive SMS texts • Ability to respond to questions and engage with “Penny” in English • Ability to provide informed consent to participate in the study • Blanket approval from the patient’s medical oncologist to be approached
Interventions	
 • Treatment Arm: Patients in the treatment arm will receive access to the mobile phone-based intervention (“Penny”). Penny is a conversational agent (“chatbot”) that engages patients in real time via text messaging, allowing for bidirectional communication between clinicians and patients, longitudinal symptom monitoring with self-management support, and motivational cues to promote adherence. The chatbot will remind patients how and when to take their oral targeted therapies (based on prescribed regimen) and provide self-management and monitoring of mild side effects guided by clinical pathways. • Usual Care: Patients in the usual care arm will receive standard of care for symptom monitoring and management of side effects, which includes patient education at the time of prescribing and direction to call providers or triage nurses if anything arises between appointments.
Outcomes	
 • Primary Outcome: Adherence (measured using MEMS caps) defined by the overall proportion of adherent days and classified dichotomously as adherent if total proportion of days is ≥95%

	
 • Secondary Outcomes: Persistence defined as the number of consecutive days on the regimen and conversely gaps in overall treatment • Exploratory Outcomes: Patient-reported outcomes including health-related quality of life (HRQOL), symptom burden, patient satisfaction, financial toxicity, social and behavioral determinants of health (SBDH), medication self-efficacy, and health literacy
Primary Analysis	Intent-to-treat (ITT) analyses using repeated measures logistic regression to compare the overall effect of the intervention on patient adherence
Secondary Analyses	Baseline survey and clinical data will be used to explore potential mediators and moderators of treatment effects. Standard mediation analysis will be used to explore separately whether symptom management or self-efficacy mediates treatment effects. Multivariable regression analysis with intervention, moderator, and interaction terms will be used to assess effect modification by patient characteristics based on significance of the interaction term.
Study Oversight	Trial oversight will be conducted by the University of Pennsylvania Institutional Review Board. Safety will be monitored on an ongoing basis by the co-PIs, study team, and institutional experts at Penn Medicine not directly involved in the study.

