6. RANDOMIZATION

6.1 Groups

Arm 1: Intervention Group

The intervention is an automated, text-messaging program (chatbot) named “Penny” that is guided by artificial intelligence and natural language process. Penny engages patients in real time via text messaging and continues to learn from interactions. Patients can also directly communicate with Penny at any time. Core functionalities include: (1) real-time dosing instructions, (2) motivational reminders, and (3) symptom monitoring with self-management support. Penny transmits data from text interactions into the secure online dashboard in real time, allowing for enhanced communication and longitudinal monitoring between clinicians and patients. Penny is essentially a virtual care team member, always available to support patients receiving complex oral anticancer therapies. Preliminary data from 10 cancer patients indicate that Penny helped patients to manage side effects and adherence, and can be integrated into care safely and effectively.²⁸ This project will expand upon these findings to evaluate the efficacy of Penny as a patient-directed intervention, and to explore how multilevel mechanisms may impact its acceptability and effectiveness in routine care.

Over an approximate 12-week treatment period, Penny will guide patients randomized to the treatment arm through when and how to take their oral therapies. Penny will additionally monitor patient-reported side effects based on the PRO version of Common Terminology Criteria for Adverse Events (PRO-CTCAE) grading and established clinical pathways used currently at Abramson Cancer Center to escalate and manage patient-reported symptoms (See Appendices).^{29,30} If the side effect is determined to be Grade 1-2 (mild to moderate), patients will be walked through self-care by the chatbot utilizing clinically approved and pre-determined symptom management pathways. If the side effect is deemed Grade 3 (severe) or higher or if the chatbot does not recognize the symptom to triage, the patient will be advised to call his/her care team and a real-time escalation message will be sent to the clinical

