9.2 Exploratory Analyses

In exploratory analyses, we will apply standard mediation analysis to explore separately whether symptom management or self-efficacy mediates the relationship between arm assignment and adherence. We will conduct multivariable regression to explore the following: (1) if arm assignment has an effect on symptom management or self-efficacy, (2) if either of these intermediate outcomes has an effect on daily adherence; (3) if arm assignment has an effect on daily adherence, or (4) if the effect of arm assignment on daily adherence shifts when either of these intermediate outcomes is added to the model. Rejecting the null for all four hypotheses will be necessary to support either symptom management or medication self-efficacy as a mediator. We will use a modified Sobel test for significance testing. Additionally, we will explore for potential effect modification across different patient subgroups based on patient demographics, health literacy, social determinants of health, clinical characteristics, and other factors. We will fit multivariable regression models with intervention, moderator, and interaction terms to assess potential effect modification based on significance of the interaction term. As planned analysis, we will also explore mortality differences between study arms at 6- and 12-month follow-up using data collected passively from the EHR (as outlined in the consent form).

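### The two candidate mediators are tested only in separate models, so a score with no effect of its own on adherence can pass the four-condition rule if Penny shifts both scores and they correlate within arm

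*Combined protocol and SAP*

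**What the plan says.** The Secondary Analyses entry of the Protocol Summary says: "Standard mediation analysis will be used to explore separately whether symptom management or self-efficacy mediates treatment effects". Section 9.2 says the same: "we will apply standard mediation analysis to explore separately whether symptom management or self-efficacy mediates the relationship between arm assignment and adherence". It then lists four regressions. The fourth asks "if the effect of arm assignment on daily adherence shifts when either of these intermediate outcomes is added to the model", so one score enters at a time. The decision rule is: "Rejecting the null for all four hypotheses will be necessary to support either symptom management or medication self-efficacy as a mediator". On testing, the plan adds: "We will use a modified Sobel test for significance testing", without saying what the modification is.

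No section describes an outcome model holding both scores, adjusts one for the other, mentions their correlation or states a causal order between them.

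Section 6.1 lists Penny's core functions as "1) real-time dosing instructions, (2) motivational reminders, and (3) symptom monitoring with self-management support". The Study Abstract attributes the expected benefit to better symptom management together with other, unnamed, behavioural determinants. Section 4.1 places the mediation question among the exploratory objectives.

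**The concern.** Randomization protects the comparison of arms, not the comparison of patients with different mediator scores. In a model with arm and one score, the omitted score is a confounder if it affects adherence and correlates with the included one. The included score then picks up part of the omitted score's effect.

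The four conditions do not screen this out once Penny moves both scores. A bystander score passes the first because arm shifts it, the second because it stands in for the real mediator, the third because the total effect of arm is the same whichever score is studied, and the fourth as a consequence of the second. Perfect timing of measurement and a linear outcome scale would not help.

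At stake is the reading of the mechanism. Two positive single-mediator results could be reported as two distinct routes by which Penny works when there is only one, and that could misdirect later development of the chatbot.

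**Working it through.** **Inputs from the documents.** Section 5.5 gives 170 patients, 15% loss, 72 per arm (170 × 0.85 = 144.5, stated as 144), control adherence of 65.5%, a 20.9-point difference (so 86.4% under Penny), Fisher's exact test and 80% power. No alpha is stated; two-sided 0.05 is assumed. Exact enumeration of the two-sided Fisher test with 72 per arm gives 80.03%, so the plan's figure reproduces. The plan gives no figure for the mediation analysis.

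**Inputs assumed, because the documents give none.** Both scores have within-arm SD 1 and correlation r. Penny shifts the true mediator M1 by a₁ = 0.5 SD and the inert score M2 by a₂ = 0.5 SD. M1 acts on adherence with b₁ = 0.4 SD per SD; M2 has no effect. The total arm effect is set to 80% power on a continuous patient-level outcome: (1.960 + 0.842) × √(2/72) = 0.467 SD. The classic Sobel test is used and also stands in for the fourth condition.

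**Expected bias.** In the model with arm and M2 only, the M2 coefficient tends to r × b₁, so the apparent indirect effect of M2 is a₂ × r × b₁ = 0.5 × 0.4 × r = 0.20r.

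| r | apparent indirect effect of M2 | share of 0.467 |
|---|---|---|
| 0.3 | 0.06 | 13% |
| 0.5 | 0.10 | 21% |
| 0.7 | 0.14 | 30% |

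M2's indirect effect given M1 is 0.

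**How often M2 passes every condition** (Monte Carlo, several thousand trials per setting; the range at 0.5 is across repeated runs):

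| r | separate models | joint model |
|---|---|---|
| 0 | about 1% | about 1% |
| 0.3 | about 10% | about 1% |
| 0.5 | 27–30% | about 1% |
| 0.7 | about 51% | about 1% |

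With a₂ = 0.25 SD and r = 0.5, the separate-model rate falls to about 7%. If arm does not move M2 at all (r = 0.5), it is 4% or less, because the first condition blocks it.

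**Check on the plan's own outcome scale.** Daily adherence over 84 days was simulated so that 65.5% and 86.4% of patients reach the 95% threshold, and fitted by logistic GEE. Assumed ranges: arm effect on the scores 0.5 or 0.8 SD, share mediated by M1 30% or 60%, between-patient SD 1.5 or 2.0 on the logit scale. With equal shifts in both scores, M2 passes in 2–4% (r = 0), 7–33% (0.3), 15–67% (0.5) and 26–81% (0.7) of trials. If arm moves M2 only by r times its effect on M1, the rates are 3% or less (0.3), 4–23% (0.5) and 18–66% (0.7). The joint model stays at or below about 5% in every setting.

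**The same data under a different causal order.** Suppose self-efficacy (M2) acts through symptom management (M1): M2 raises M1 by r per SD, and arm raises M1 directly by the remaining 0.5 − 0.5r. The genuine effect through M2 is then 0.5 × r × 0.4 = 0.20r, identical to the value in the first table. Separate testing supports this real mediator in about 30% (path 0.5) and 52% (path 0.7) of trials; the joint model supports it in about 1%.

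**The case against.** Three objections have force.

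First, a reader might infer that separate testing is simply wrong and should be replaced. The documents do not support that, because they do not say the two scores act in parallel. If self-efficacy works through symptom management, the data look the same, the separate model is the correct one, and a joint model used alone would dismiss a real pathway. This stands, and it is why the separate models should stay.

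Second, a reader might infer that a bystander will usually be declared a mediator. The documents give no correlation, no arm-to-score effect and no mediated share. Across the settings run with equal shifts, the rate goes from near nominal to a large majority of trials. Correlation alone is not enough: Penny must also move the bystander score. This stands, so the claim must be conditional.

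Third, a reader might infer that Penny is built to move both scores. The summary lists "longitudinal symptom monitoring with self-management support, and motivational cues to promote adherence", which does not name self-efficacy, and section 8.2 treats Penny's effect on self-efficacy only as something for interviews to explore. It is a fair inference that both could move, since the plan tests arm effects on both, but it is no more than that.

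The plan also does not undertake to divide the effect between the scores or to add mediated shares. The analysis is exploratory within a pilot, and a joint model still leaves unmeasured mediator–outcome confounding. None of this removes the gap: as written, the plan has nothing that separates two distinct mechanisms from one mechanism seen through two correlated scores.

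**Conclusion.** The concern holds in conditional form. The rule in section 9.2 can support a score with no effect of its own when two things are both true: Penny shifts that score appreciably, and the score correlates with the real mediator within arm. At correlations of 0.5 to 0.7 with equal 0.5 SD shifts, the simple model puts this at roughly 27% to 51% of trials, against about 1% jointly; it is negligible when the scores are uncorrelated within arm.

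These figures rest on assumed effect sizes, two-sided 0.05, the classic rather than the plan's undescribed modified Sobel test, and parallel mediators. No primary or secondary conclusion depends on the analysis. This is a cheap improvement to an exploratory analysis, not a threat to the trial.

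**What to change.** In the Protocol Summary (Secondary Analyses) and section 9.2:

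- Keep the single-mediator models and add one outcome model with arm and both mediators.
- Report each specific indirect effect, the joint indirect effect and the within-arm correlation of the two scores.
- State the assumed causal order of the mediators.
- Describe a score as a distinct mechanism only if the joint model also supports it. If it is supported only separately, report that it cannot be told apart from a correlate of the other score or a pathway through it.

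The cost is a few sentences and one extra model on data already being collected. Power for the true mediator is lower in the joint model: about 66% to 64% at correlation 0.5, and 67% to 56% at 0.7, under the assumptions above. The joint model alone would miss a mediator acting through the other, so both sets of results are needed. Unmeasured confounding between mediator and adherence remains and should be stated as a limitation.

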2. STUDY ABSTRACT

The objective of this project is to identify effective strategies to help patients with lung cancer manage side effects and achieve optimal adherence to oral targeted therapies. To achieve this objective, we will evaluate the effect of a mobile phone-based intervention (“Penny”), compared to usual care, on adherence to oral targeted therapies using a two-arm randomized controlled trial (Aim 1), and explore how multilevel factors impact the acceptability and effectiveness of this strategy by collecting qualitative and quantitative data from clinicians and patients (Aim 2). Penny is a conversational agent (“chatbot”) that engages patients in real time via text messaging, allowing for bidirectional communication between clinicians and patients, longitudinal symptom monitoring with self-management support, and motivational cues to promote adherence. The chatbot will walk patients through how and when to take their oral targeted therapies (based on prescribed regimen) as well as provide self-management and monitoring of mild-to-moderate side effects guided by clinical pathways. Severe or greater side effects will be escalated to the clinical research team in real-time and then escalated to wider clinical care team using existing clinical pathways. Guided by established theory of behavior change (Information-Motivation-Behavioral Skills model), we hypothesize Penny will improve adherence to oral targeted therapies by improving patient-level symptom management and other determinants of behavior change. Primary outcomes (adherence and persistence) will be measured using microelectronic monitoring system (MEMS) caps. Secondary outcomes will be assessed using longitudinal surveys and medical record data. Semi-structured interview data will also be collected from a subsample of 60 patients and clinicians following the intervention period. By combining innovations from behavioral economics and machine learning with a highly accessible text-messaging platform, our project has the potential not only to identify scalable, patient-targeted strategies for improving symptom management and adherence to targeted therapies, but also to transform the way cancer care is delivered.

3. BACKGROUND AND RATIONALE

The availability and use of oral anticancer agents have grown substantially over the past decade, especially for patients with lung cancer. There are currently more than 50 approved oral targeted therapies, fourteen of which are approved for use in patients with advanced non-small cell lung cancer.

Most patients with cancer prefer oral to infusion-based therapies, provided equivalent efficacy and toxicity,¹ as oral agents reduce the burden of care with convenient dosing outside of the clinic.² However, home administration shifts the responsibility of symptom monitoring and adherence to patients and their caregivers. Because treatment efficacy depends on proper use, identifying effective strategies to ensure adherence to oral therapies is vital.

Even among cancer patients, non-adherence remains a significant problem.³ Studies have shown widely variable rates of adherence to oral therapies, from 16%-105% depending on malignancy, medication, assessment, and study follow-up.^{4,5} In the context of lung cancer, suboptimal adherence affects a considerable number of patients: up to 14.3 percent of patients fall below a 80% adherence rate and 21% do not take their medication as prescribed, according to recent studies.^{1,6,7} Suboptimal adherence is associated with worse outcomes,⁸ including cancer progression,⁹ inferior survival,¹⁰ higher toxicities,¹¹ and higher resource utilization and spending.¹² Reasons for non-adherence include patient, clinician, disease, treatment, and healthcare system factors.¹³ Patient-level factors including inadequate understanding of complex dosing instructions,¹⁴ limited ability to manage side effects,⁴ financial costs,¹⁵ and poor patient-clinician communication have been particularly hard to address. There is limited research on patient-level strategies to improve medication adherence in patients with advanced lung cancer. Small studies have evaluated the use of patient- and clinician-targeted strategies including enhanced patient education and treatment monitoring.^{16,17} However, these were limited by small sample size and non-randomized design.

Patient-directed intervention to improve symptom management and adherence should be theoretically based and scalable. Behavioral economic theory holds that to affect a frequent behavior such as taking daily medication, the implementation strategy must engage at nearly the same or greater frequency.¹⁸ For complex regimens or those regimens with significant side effects, this degree of engagement would have been impossible before the era of connected devices. However, modern technology allows for ‘automated hovering’—patient surveillance outside of clinical settings—which can deliver implementation strategies in real time.¹⁹ A small but growing literature supports digital interventions across a variety of chronic illnesses,^{20,21} including cancer.²² Today, technology-based approaches to aid adherence are feasible and safe, but their efficacy has not been rigorously studied.²³ Across the digital health landscape, conversational agents—or technologies that draw upon augmented or artificial intelligence and natural language processing to mimic human conversation and are promising to support behavior change.

Low-cost, technology-based approaches such as text messaging have shown promise as sustainable and scalable patient-directed strategies to improve adherence, particularly in low-resource settings.²⁴ Yet for oral targeted therapies, these strategies have not been extensively studied.²⁵ For patient populations outside of oncology, text-based and other digital strategies guided by insights from behavioral economics have been effective in improving symptom monitoring and adherence.²⁶ In this project, we will test a novel, technology-based intervention (“Penny”), engineered using principles from behavioral economics to improve symptom management and medication adherence among patients with advanced lung cancer taking oral targeted therapies. Guided by an established theory of behavior change, we hypothesize Penny will improve adherence to oral therapies by improving patient-level symptom management and other determinants of behavior change.

4. OBJECTIVES

The overall goal of our project is to identify effective strategies for improving lung cancer outcomes by helping patients to better manage symptoms and adhere to oral therapies.

4.1 Specific Aims

The specific aims of this single center pilot randomized project are to:

Aim 1. To evaluate the effect of a mobile phone-based intervention (“Penny”), compared to usual care, on patient adherence to oral targeted therapies using a two-arm randomized-controlled trial. Patients with lung cancer receiving oral targeted therapies at UPHS will be randomized (1:1) to Penny or usual care.

Aim 2. To use mixed methods approaches with clinicians and patients to explore factors shaping the acceptability, effectiveness, and future implementation of Penny into routine cancer care. Following active intervention, semi-structured interview and questionnaire data will be collected from a stratified subsample of 30 patients enrolled in the trial and 30 clinicians and staff who provide oncology care at Penn Medicine.

In addition primary aims, we will also explore: 1) the impact of the intervention on patient-reported outcomes including patient satisfaction, medication self-efficacy, and other outcomes; 2) if symptom management or self-efficacy mediates the relationship between arm assignment and adherence; and 3) any potential effect modification across different patient subgroups based on patient demographics, health literacy, social determinants of health, clinical characteristics, and other factors.

